24. The subject has osteoporosis defined as a bone density T score of ≤ -2.5 . (A screening Questionnaire for osteoporosis, SCORE (Simple Calculated Osteoporosis Risk Estimation) and MORES (Male Osteoporosis Risk Estimation Score), will be used to screen patients who require a DEXA bone mineral density measurement.

Timeline:	Initial Enrollment:	10/2012
	Last Enrollment:	12/2017
	Last Subject Visit	7/2019
	Last Close-out Visit	10/2019
Study Duration:	
The length of the Study will be 24 months post-operative*.
 
V 1 Screening : -21 days to day 0
 
V2 Surgery: day 0
 
V3 Post-op: 3 months =90 days +/- 14 days
 
V4 Post-op: 6 months = 180 days +/- 30 days
 
V5 Post-op: 12 months =360 days +/- 60 days
 
V6 Post-op: 24 months = 720 days +/- 60days
 
* If the study is prematurely terminated the investigator will promptly inform active subjects to ensure adequate follow-up for the subjects according to their standard of care practices.
	
Monitoring:	
ArthroX Clinical Research [name] [name] Ph.: [contact]
	

2 Introduction

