3.2.2 Primary Endpoint

The primary safety and effectiveness endpoint is 2 Year Composite Clinical Success requiring the following:

- An improvement in the Adjusted Constant Score (for pain, function and range of motion) from baseline (pre-op) to the Month 24 time-point that is ≥ 10 points and a final Adjusted Constant Score ≥ 54 .

- Radiographic success at the Month 24 time-point which is defined as absence of clinically significant humeral radiolucency, humeral migration/subsidence (relative to 3 month time point), glenoid radiolucency, glenoid migration/subsidence (relative to 3 month time point), device disassembly or fracture, and/or periprosthetic fracture, as described in the radiographic protocol
- No reoperation, removal, or modification of any study component up to the subject's completion of the study.
- No serious device-related complications up to the subject's completion of the study.

For a patient to be considered a success, he or she must meet all of the above criteria.

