4.1.2 Per Protocol (Efficacy Evaluable) Cohort

Patients included in the ITT cohort but found to have been randomized in error will be excluded from the Per Protocol (Efficacy Evaluable) cohort. A patient will be considered to have been randomized in error if it is determined that the patient has clinically significant violations of the inclusion or exclusion criteria. Because approval and labeling is sought for patients meeting study inclusion and exclusion criteria, primary non-inferiority testing will be conducted in the Per Protocol (Efficacy Evaluable) cohort. Safety endpoints will be summarized for the Per Protocol cohort for the same reason. However, all adverse events that occur in the study will be reported in safety listings based on the ITT cohort.

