Should subject discontinuation occur the reason(s) for discontinuation must be documented in the source documents along with notification to ArthroX Clinical Research. Once the End of Study form is completed in the EDC, the subject status will update to “Early Termination”

Subjects who are determined to be “Early Termination” from the study will not be replaced.

Complete:

Subjects that are screened, randomized, implanted with the Univers II or the Eclipse and completed the 24 month (720 days +/- 60days) follow up Visit 6 will be considered Complete.

- Once the data for visit 6 is entered in the EDC and the End of Study form, the subject status will update to complete.

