9.3 Adverse Event and Unanticipated Adverse Device Effect Reporting

At every subject encounter, the investigator will determine if there has been an adverse event since the last encounter.

For this study, serious adverse events must be reported immediately (within 24 hours) directly to ArthroX, Inc. by completing the Adverse Event form and entering it into EDC. At the time of the initial report, the outcome (resolution status) may not be known. Updated information must be entered into EDC until final resolution of the event.

Unanticipated Serious Adverse Device Effects must also be reported by the investigator to the approving IRB as soon as possible, but not later than 10 working days after the investigator first learns of the effect. The sponsor must report to the FDA, all reviewing IRBs and participating investigators within 10 working days of notification from the investigator of a USADE.

The medical monitor will provide medical surveillance on adverse events and will evaluate all Serious Adverse Events (SAEs).

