5. Lack of serious device related complications (defined as a severe device-related adverse event) up to the subject's completion of the study.

Per the World Health Organization Definition of adverse events, a Grade 3 (or severe) adverse event significantly limits the patient's ability to perform routine activities despite symptomatic therapy.

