10.7 Safety Analysis

All safety endpoints will be summarized separately for investigational and control groups. Similarly, listings with details of the specific complications will be summarized separately as well.

The CCS Component Safety endpoint is any serious, definitely device-related adverse event within 24 Months of surgery. This will be evaluated at the exact two year anniversary (i.e., relative day 730) after the implantation surgery. The safety hypothesis of investigational verses control equality in the likelihood of serious device-related adverse event will be tested using a two-sided Fisher's Exact Test with Type I error rate set to $\alpha=0.05$.

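### Section 10.7 tests serious device-related events to day 730 on counts without saying how patients observed for less than 730 days are counted; a Kaplan-Meier day-730 rate should be added

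*Combined protocol and SAP*

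**What the plan says.** Section 10.7 (Safety Analysis) defines the component safety endpoint as a serious, definitely device-related adverse event within 24 months and fixes the time point: "This will be evaluated at the exact two year anniversary (i.e., relative day 730) after the implantation surgery". The comparison is that the likelihood of a "serious device-related adverse event will be tested using a two-sided Fisher's Exact Test with Type I error rate set to" 0.05. No estimator, denominator or censoring rule follows.

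On the cohort, section 4.1.2 says "Safety endpoints will be summarized for the Per Protocol cohort for the same reason". Membership of that cohort turns on eligibility violations, not on completed follow-up.

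The documents disagree on when counting of events stops. Section 10.7 and the Primary Objective in section 1 use the exact second anniversary of surgery. Section 3.2.2 has "No serious device-related complications up to the subject's completion of the study", and the CCS component list under section 10.1 has "Lack of serious device related complications (defined as a severe device-related adverse event) up to the subject's completion of the study".

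On follow-up, section 1 (Study Duration) gives "V6 Post-op: 24 months = 720 days +/- 60days", and section 6.1.3 says that subjects who "completed the 24 month (720 days +/- 60days) follow up Visit 6 will be considered Complete". Section 9.3 ties event collection to contacts: "At every subject encounter, the investigator will determine if there has been an adverse event since the last encounter". Early terminations are not replaced (section 6.1.3). The 15% inflation in section 10.4 covers loss to follow-up and protocol-violation exclusions together. Section 3.1 ends the study on 510(k) clearance.

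**The concern.** A Fisher test compares counts over fixed denominators. If a patient whose last adverse event review was on day 400 or day 670 stays in the denominator, the unobserved days to 730 count as event-free. The crude proportion is then not the two-year risk but something smaller, in both arms.

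The plan recognises this problem elsewhere. Section 10.6 notes that numbers at risk fall over time and plans life tables, Kaplan-Meier curves and a log-rank test, but for device failures. That term is not defined and cannot be assumed to cover serious device-related events. Section 10.8 deals with missing CCS only. Section 10.7.1 gives event counts by interval, with no mention of numbers at risk.

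At stake is the accuracy of any two-year safety rate quoted from these counts. The error runs in one direction, towards a safer-looking device.

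**Working it through.** **The plan's own figure.** Section 10.7 gives no rate, sample size or power, so the only figures to reproduce are those of section 10.4. With 0.88 in both arms, margin 0.10 and one-sided 0.05, SE = √(0.88×0.12/98 + 0.88×0.12/196) = 0.0402, and power = Φ(0.10/0.0402 − 1.645) = 80.0%. Inflation: 98/0.85 gives 116 and 196/0.85 gives 231, together 347. Both reproduce.

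**Inputs.** From the documents: day 730, a Visit 6 window of days 660 to 780, and the 15% allowance. Assumed: true day-730 risk R of 3% or 10% in both arms (no rate is given); dropout timing; Visit 6 timing; all Per Protocol patients kept with events as observed.

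**Model.** Risk by day T is F(T) = 1 − exp(−H·(T/730)^k), with H = −ln(1 − R). k = 1 is a constant hazard and k = 0.5 a front-loaded one.

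**Step 1: dropout only.** Take the whole 15% as dropout spread evenly over days 0 to 730. Crude rate = 0.85·R + 0.15·mean F(T).
- R = 10%, k = 1: mean F = 5.09%, so 8.50% + 0.76% = 9.26%, which is 7.4% low.
- R = 10%, k = 0.5: mean F = 6.75%, so 8.50% + 1.01% = 9.51%, which is 4.9% low.
- R = 3%: 2.78% (k = 1, 7.5% low) or 2.85% (k = 0.5, 5.0% low).

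**Step 2: visit window only.** Spread Visit 6 evenly over days 660 to 780 and stop event collection there. Then (730 − 660)/120 = 58% of patients stop before day 730. The crude rate is the mean of F(min(T, 730)).
- R = 10%: 9.73% or 9.87%.
- R = 3%: 2.92% or 2.96%.
- Relative shortfall: 1.4% to 2.8%.

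**Step 3: both together.** Crude rate = 0.85·(step 2 rate) + 0.15·mean F(T).
- R = 10%, k = 1: 0.85×9.73% + 0.15×5.09% = 9.04%, about 1.0 point low. With k = 0.5: 9.40%, 0.6 points low.
- R = 3%: 2.71% or 2.82%, 0.3 or 0.2 points low.
- Relative shortfall: 6% to 10%. Exponential dropout with a constant hazard gives about the same, 9.02% for a true 10%.

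**Step 4: against sampling error.** At 10%, the SD of a proportion is √(0.1×0.9/196) = 2.1 points for Eclipse and √(0.1×0.9/98) = 3.0 points for control. Both exceed the largest bias above.

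**Step 5: the test and the alternative estimate.** Simulations used 231 v 116 patients, a true 5% in both arms and 2,000 runs per case.
- 15% dropout in both arms: crude rates average 4.5% and Kaplan-Meier day-730 rates 5.0% to 5.1%. Fisher rejects in 3.6% of runs, the same as with no dropout.
- 25% v 10% dropout: crude rates average 4.25% v 4.68%, a false difference of 0.43 points, while Kaplan-Meier gives 5.0% v 5.1%. Fisher rejects in 4.5% of runs.
- A plain normal test on the Kaplan-Meier difference rejects in 6.5% of runs at 15% dropout. That is a reason to keep Fisher as the formal test.

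**Step 6: numbers left at day 730.** Under step 3, 0.85×(780 − 730)/120 = 35% of patients are still observed: about 82 of 231 Eclipse and 41 of 116 controls, before removing those with events.

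**The case against.** Section 10.7 names a test, an endpoint and a time point, and nowhere says that the two-year rate will be estimated as a crude proportion over all Per Protocol patients. This stands. A reader might infer crude estimation as the stated plan. The documents support only that the test uses counts and that the counting rule is missing.

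If events are in fact ascertained to the exact anniversary, step 2 disappears. That also stands. But no adverse event review is scheduled after Visit 6, and the documents conflict on the stopping point, so the rule has to be written down.

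The 15% also covers eligibility exclusions, so it is an upper bound on dropout as planned. With similar follow-up the bias largely cancels between arms. Events are also counted by interval and listed for the ITT cohort. All this stands and limits the size of the point.

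A stronger reading is that the control halt near 77 (section 3.1) and early 510(k) clearance would depress the Eclipse rate in particular. Halting control randomization shortens nobody's follow-up. The effect needs late Eclipse-only patients to be cut short, and the documents do not say when clearance might come. The section 1 timeline leaves 577 days from the end of December 2017 to the end of July 2019, but gives no enrolment pace by arm. Even if 196 − 2×77 = 42 of 196 Eclipse patients had only 592 days, the loss at a true 10% would be 0.2 to 0.4 points.

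**Conclusion.** The point holds as a minor one. Section 10.7 leaves the counting of patients with less than 730 days undefined, and nothing else in the plan fills the gap. On the natural reading, with all Per Protocol patients kept, the crude two-year rate is about 6% to 10% low in relative terms in both arms when dropout and the visit window act together.

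The upper figure rests on a constant hazard, the full 15% being dropout, and event recording that stops at Visit 6. Less dropout or more front-loaded events shrink it; substantially unequal dropout would add a small false difference between arms.

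A reader might infer that the Fisher test is invalid or that the safety conclusion would change. The calculations do not support that: the bias is below sampling error, and in the cases with equal true risk the rejection rate stayed near or below 5%. What is affected is the rate that is quoted.

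**What to change.** In section 10.7:
- Keep the Fisher test on all Per Protocol patients with events as observed, and state that denominator. Do not restrict it to patients with an event or observation to day 730: those with events would stay in while many event-free patients dropped out, which inflates the rate.
- Settle the end of ascertainment as day 730, and align sections 1, 3.2 and 10.1 with it.
- Add for each arm the Kaplan-Meier cumulative incidence of first serious device-related event to day 730, censored at the last contact with adverse event review, using the methods already in section 10.6.
- Use an interval suited to few events (log-log or Wilson-type).
- State that censoring is assumed non-informative, and say how deaths are handled (censored or treated as a competing event).
- Report the number at risk and follow-up completeness to day 730 by arm.

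The cost is a few sentences and one table, from event and visit dates already collected; the formal test does not change. The downsides are rough intervals with few events, a thin risk set at day 730, and slightly higher quoted rates.

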10.7.1 Adverse events counts over time

The numbers of specific adverse events occurring pre-discharge and for each study interval will be summarized separately for each relevant cohort. Counts

of systemic adverse events will be summarized on a per patient basis. All other adverse events will be summarized on a per procedure basis.

10.7.2 Adverse event detail listings

Adverse events listings will be provided for all patients in the ITT cohort and will provide details regarding adverse event type, relation to shoulder procedure, action taken, and clinical outcome. Separate listings will be constructed for adverse events with “definite” relationship to the device, “severe” adverse event, “severe device-related”, serious adverse events, and for all adverse events. The listing for all adverse events will be sorted by adverse event type.

Additional listings will be provided that include all adverse events among procedures requiring revision, removal, or replacement and all adverse events among patients who died.

10.8 Treatment of Missing Data

As previously described, patient success will be defined at Month 24 postoperatively on the basis of a Composite Clinical Success (CCS) criterion. If the Month 24 CCS endpoint is missing due to a clinical evaluation (i.e., Constant score or radiographic results) unavailable at the Month 24 interval but available at a later date (i.e., after the end of the Month 24 interval), the later clinical evaluations will be used to impute missing values. The roll-back imputation is typically considered conservative since in most orthopedic study, maximum recovery is achieved earlier than 24 Months.

It is expected that there will be at least a few patients with missing Month 24 CCS despite the use of Month 24+ roll-back for clinical and radiographic components of the Month 24 CCS. A tipping point analysis will be performed in order to assess the impact of missing data on primary non-inferiority comparisons. Sequentially, at each stage of the tipping point analysis, one missing Month 24 CCS in the investigational device group will be considered as a failure while at the same time one missing value in the control group will be considered a success. Tipping point stages will be sequentially assessed until there are no more missing CCS values in either group.

If the percentage of missing CCS is more than small, e.g., >10%, then the primary sensitivity analysis will involve multiple imputation (Rubin DB, 1991) (MI) rather than tipping point analysis.

MI minimizes the effects of selection bias on the estimates of the proportions achieving Month 24 CCS. A logistic regression method for monotone missing data using SAS procedure Proc.MI (SAS Institute INC, 2006) will be employed to produce multiply imputed outcome determinations for patients missing Month 24 CCS. This method first fits a

logistic regression model for the outcome variable based on covariates using complete cases. Then, based on the fitted regression model, a new logistic regression model is simulated from the posterior predictive distribution of the parameters which is then used to impute the missing outcome variables. This is done by using the model to compute the expected probability of clinical success for each patient missing the outcome. A uniform random number from 0 to the patient specific expected probability is then generated and if the value is less than the expected probability, the outcome is imputed as a success, otherwise impute the outcome as failure. After all missing outcomes are imputed, the estimated proportion and its standard error will be determined in the usual way. This process will be repeated 20 times. The final point estimate will be determined as the mean value over these 20 multiple imputations. The final standard error used to construct the 95% confidence interval needed for the primary non-inferiority test will be determined from the pooled variance (within imputation variance) plus a term reflecting variability among the 20 multiply imputed point estimates (between imputation variance) (Rubin DB, 1986). The final estimate and 95% confidence interval will be computed by the SAS procedure Proc.MIANALYZE using this approach. By imputing the missing values among patients with missing Month 24 CCS, bias is reduced since the inference is to the entire population that includes patients both missing and not missing Month 24 CCS. The standard error of the final estimate accounts for the statistical uncertainty present in the imputed outcomes and so confidence intervals tend to have the correct coverage rates.

11 Bibliography

Blackwelder, W. (1982). Proving the null hypothesis. *Controlled Clinical Trials*, 3:345-353.

Bohsali KI, W. M. (2006). Complications of total shoulder arthroplasty. *J Bone Joint Surg* , 88, 2279-2292

Boileau, P., et al., *Cemented polyethylene versus uncemented metal-backed glenoid components in total shoulder arthroplasty: a prospective, double-blind, randomized study*. *J Shoulder Elbow Surg*, 2002. **11**(4): p. 351-9.

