3.1 Study Design

Prospective, randomized, multi-center, clinical study. Up to twenty centers will randomize up to 350 subjects who are candidates for a Total Shoulder Arthroplasty, to 2 treatment groups in a 2:1 (Eclipse: Univers II) fashion. FDA has agreed that randomization of controls may be halted after N=77, with continuing enrollment of Eclipse until the originally planned Eclipse sample size target is reached. Given the timing needed for approval to stop control enrollment, the actually number of evaluable randomized controls may be slightly larger. This study will cease enrollment and be terminated if the Eclipse Shoulder Prosthesis receives 510 (k) clearance prior to all subjects completing the study.

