10.4 Sample Size Analysis for Primary Non-Inferiority Test

Given the above criteria, the Sponsor expects a success rate of 88% for both the Eclipse and control group.

To determine the required sample size, it was assumed that the above primary hypotheses will be tested using 1-sided $\alpha=0.05$ at a statistical power of at least 80%. Under these assumptions, nQuery Advisor 7.0 module PTE0U-1 produces the following:

“When the sample sizes in the groups are 98 and 196, a two-group large-sample normal approximation test of proportions with a one-sided 0.05 significance level will have 80% power to reject the null hypothesis that the test and the standard are not equivalent (the difference in proportions, $p_T - p_S$, is -0.10 or farther from zero in the same direction) in favor of the alternative hypothesis that the proportions in the two groups are equivalent, assuming that the expected difference in proportions is 0.00 and the proportion in the standard group is 0.88.

Therefore, the total number of Per Protocol (Efficacy Evaluable) patients required under these assumptions are $N=294$. The number of protocol violations of inclusion / exclusion criteria (i.e., randomized in error) is expected to be small. The randomized sample size is adjusted up by 15% to account for both loss-to-follow-up and exclusions due to protocol violation to $N=347$.

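### As worded, the multiple-imputation draw in section 10.8 makes every missing Month 24 CCS a success, because the uniform number is capped at the patient's own predicted probability

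*Combined protocol and SAP*

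**What the plan says.** Section 10.8 (Treatment of Missing Data) first rolls back evaluations made after the Month 24 interval, then plans a tipping-point analysis. Above a threshold it switches method: "If the percentage of missing CCS is more than small, e.g., >10%, then the primary sensitivity analysis will involve multiple imputation". The method named is "A logistic regression method for monotone missing data using SAS procedure Proc.MI".

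The section then sets out the steps. A logistic model is fitted to the complete cases, a new model is simulated from the posterior, and each patient with a missing outcome receives a predicted probability of success. The range of the draw is given as follows: "A uniform random number from 0 to the patient specific expected probability is then generated". The decision rule applied to that draw reads: "if the value is less than the expected probability, the outcome is imputed as a success, otherwise impute the outcome as failure". This is done 20 times and the results are pooled with within- and between-imputation variance.

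The section claims that "The standard error of the final estimate accounts for the statistical uncertainty present in the imputed outcomes". It describes the pooled standard error as "The final standard error used to construct the 95% confidence interval needed for the primary non-inferiority test".

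**The concern.** To impute a binary outcome with success probability p, one draws a uniform number on (0,1) and calls it a success if it falls below p. The text instead draws on (0, p) and compares the result with p. The comparison is then always true and the failure branch can never be reached.

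Followed literally, this is not multiple imputation. It is a single deterministic imputation of success for everyone missing, repeated 20 times. It contradicts the section's own statements that bias is reduced and that the standard error carries the imputation uncertainty.

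What is at stake is the analysis meant to show whether the non-inferiority result survives missing data. When Eclipse is truly worse, or has more missing outcomes, counting every missing patient as a success pulls the difference towards non-inferiority. It also makes the standard error too small in every case.

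**Working it through.** **The plan's own figure.** Inputs from section 10.4: 88% success in both arms, margin 0.10, one-sided 0.05, 98 control and 196 Eclipse.

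- SE = sqrt[0.88 × 0.12 × (1/98 + 1/196)] = 0.0402
- Power = Φ(0.10/0.0402 − 1.645) = 80.0%, as stated
- With 15% added for loss: 98/0.85 → 116 and 196/0.85 → 231, total 347, as stated

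These numbers are not in dispute; 231/116 is used below.

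**The draw.** If U is uniform on (0, p), then U/p is uniform on (0,1), so P(U < p) = P(U/p < 1) = 1 for any p > 0. Simulation with 2,000,000 draws at each of p = 0.05, 0.30, 0.50, 0.70, 0.88 and 0.95 gave a success share of 1.000 every time under the written rule. With a draw on (0,1) the shares were 0.050, 0.300, 0.500, 0.700, 0.880 and 0.950.

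**Variance.** With 20 identical data sets the between-imputation variance B is 0, so the total W + (1 + 1/20)B reduces to W, the variance of a trial with no missing data.

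**Shift in the difference.** Let m be the missing fraction in an arm, missing completely at random. The written rule turns a true rate p into (1 − m)p + m, so the difference moves by

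m_E(1 − p_E) − m_C(1 − p_C).

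At 78% vs 88% (exactly on the margin):

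- 15% in each arm: 0.15 × 0.22 − 0.15 × 0.12 = +0.015, so −0.100 becomes −0.085
- 18% Eclipse, 9% control: 0.0396 − 0.0108 = +0.0288, so −0.0712
- 9% Eclipse, 18% control: 0.0198 − 0.0216 = −0.0018, so −0.1018

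At 88% vs 88% with equal missingness the shift is zero.

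**Chance of declaring non-inferiority.** Simulation: margin 0.10, unpooled Wald SE, 400,000 trials per scenario. The correct imputation used 40,000 trials, 20 imputations, a logistic intercept per arm drawn from its approximate posterior, and Rubin pooling. Each pair is one-sided 0.05 / lower limit of the 95% interval that section 10.8 names.

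| True rates | n (Eclipse/control) | Missing (Eclipse/control) | Written rule | Complete case | Correct draw |
|---|---|---|---|---|---|
| 78 vs 88 | 231/116 | 11%/11% | 7.8% / 4.1% | 4.4% / 2.1% | 4.5% / 2.1% |
| 78 vs 88 | 231/116 | 15%/15% | 9.6% / 5.1% | 4.4% / 2.1% | 4.4% / 2.1% |
| 78 vs 88 | 231/116 | 18%/9% | 17.3% / 10.3% | 4.6% / 2.2% | not run |
| 78 vs 88 | 231/116 | 9%/18% | 4.0% / 1.9% | 4.4% / 2.0% | not run |
| 78 vs 88 | 231/77 | 15%/15% | 7.9% / 3.9% | 3.9% / 1.7% | not run |
| 88 vs 88 | 231/116 | 15%/15% | 92% / 85% | 82% / 72% | 82% / 72% |

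The first five rows are false-positive rates; the last is power. The 77-control row is included because section 3.1 records that "FDA has agreed that randomization of controls may be halted after N=77". In the last row the mean SE is 0.034 under the written rule and 0.040 with a correct draw, so the extra power comes from treating unobserved outcomes as known successes.

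**The case against.** The strongest reply is that the plan commits to SAS Proc MI, and that the hand-written steps only describe what that procedure does. The surrounding text shows the intent: it has a failure branch, 20 repetitions and a between-imputation term, all pointless under the literal draw. Anyone who coded it would see 20 identical data sets. This largely stands as a statement about what will probably be run. It does not make the text right. The steps are given as the method, the plan does not say which governs if procedure and prose differ, and someone replicating from the document would reproduce the error.

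Second, reach. Multiple imputation leads only above about 10% missing CCS, after roll-back has recovered late evaluations. At or below that the tipping-point analysis applies and is unaffected. This stands: the table shows pass rates of a conditional sensitivity analysis, not the trial's error rate. The section does blur the matter by tying the interval to the primary test.

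Third, the larger figures depend on assumptions. No document gives missing rates by arm, and the 18%/9% split is illustrative only. The 15% is probably high, since "The randomized sample size is adjusted up by 15% to account for both loss-to-follow-up and exclusions due to protocol violation" covers exclusions as well as loss. On the 95% limit, the equal-missingness results (3.9% to 5.1%) sit at or near the one-sided 5% of section 10.4. That also stands, although they are about double what a correct draw or complete-case analysis gives. With 77 controls and 11% missing per arm, the written rule gives 6.5% / 3.1%. Patients with an earlier reoperation or serious device-related complication are already failures and need no imputation, which missing completely at random ignores.

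**Conclusion.** The concern holds. The rule as written cannot impute a failure; that follows from the wording and rests on no assumption. The zero between-imputation variance, and the conflict with the section's claim about the standard error, follow from it.

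The practical effect is conditional on three things: missing CCS exceeding about 10%, the written steps being coded in place of the built-in Proc MI method, and the pattern of missingness. Under equal missingness of 11% to 15% and a true difference at the margin, the false-positive rate of this analysis roughly doubles. It rises further if Eclipse has more missing data, and does not rise under the reverse 9%/18% split. The bias goes against Eclipse when Eclipse is truly better with equal missingness, or when enough more control outcomes are missing. The figures assume data missing completely at random and all randomised patients in the analysed cohort. It should be fixed: the wording error is certain and its effect on the analysis is possible but not shown.

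**What to change.** In section 10.8, replace the sentence describing the draw with:

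> A uniform random number on (0,1) is generated; if it is less than the patient's expected probability of success, the outcome is imputed as a success, otherwise as a failure.

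Alternatively, state that the Proc MI logistic method governs and delete the hand-written draw. Either change makes the description agree with the pooling and the standard-error claim that follow it.

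The cost is one sentence of analysis-plan wording, with no new data, no change to sample size and negligible programming.
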